9.2 SETTING

The NIS will be conducted in about 25-30 sites globally which are experienced in lung cancer treatment. An average of 8-10 patients per site (with a maximum of up to 15 patients per site) is expected.

Patient participation in this NIS is voluntary. Patients were treated and are treated according to the standard of care independent of patient's consent to participate in this NIS.

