9.2.1 Selection of study population

Site selection:

Sites in countries with launch dates prior to 1st Jan 2015 and known to prescribe Gi(l)otrif[®] on a regular basis will be chosen. Asian and Non-Asian countries will be included.

Inclusion criteria:

All consecutive patients will be included if all the following criteria are present:

- Age \geq 18 years

Protocol for non-interventional studies based on existing data

BI Study Number 1200.270

c09038525-01

Proprietary confidential information © 2016 Boehringer Ingelheim International GmbH or one or more of its affiliated companies

- Patients with EGFR mutation (common mutations), TKI-naïve advanced NSCLC, treated with Gi(l)otrif[®] as the first-line treatment for NSCLC within the approved label
- Signed and dated written informed consent per regulations. (Exemption of a written informed consent for retrospective observational studies in some countries per local regulations and legal requirements.)

Exclusion criteria:

Patient won't be included if any of the following criteria is present:

- Any contraindication to Gi(l)otrif[®] as specified in label.
- Patients with uncommon mutations are excluded as uncommon mutations are not within label in all participating countries (e.g. USA).
- Patients still on treatment with Gi(l)otrif[®] will be excluded unless treatment period is ≥ 6 months.
- Patients treated with Gi(l)otrif[®] within an interventional trial.

A log of all patients included into the study will be maintained in the ISF at the investigational site.

Patients treated with Gi(l)otrif[®] in interventional trials are excluded to ensure the non-interventional setting of this study. The threshold of ≥ 6 months treatment with Gi(l)otrif[®] for patients being still on treatment was chosen to avoid early censoring and enable collection of mature data on ADRs and treatment duration. However, patients who stopped Gi(l)otrif[®] < 6 months will be included to avoid bias. All patients fulfilling inclusion and exclusion criteria from a site will be entered to avoid bias. The maximum of 15 patients per site was chosen to avoid bias by high proportion of patients coming from one site.

BI reserves the right to discontinue the study overall or at a particular study site at any time for the following reasons:

1. Failure to meet expected enrolment goals overall or at a particular study site.

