9.9 LIMITATIONS OF THE RESEARCH METHODS

The generalization and consequently the external validity of the study results, may be limited by the participation in the study of only sites that prescribe Gi(l)otrif[®] on a regular basis to ensure sufficient patient recruitment. Patients treated by investigators with less experience might experience more side effects during their treatment with Gi(l)otrif[®].

Methodological efforts have been taken to minimize selection bias: these efforts include the recommendation to include consecutive patients meeting each of the inclusion criteria and none of the exclusion criteria. In addition, this possible selection bias may be limited by the retrospective aspect of the data collection, data that have been already collected at the time of the study. Linked to this aspect is then the limitation due to data availability. Indeed, no additional data will be collected for the study purpose. So if the data is not available in the patient files, then this will be considered as missing data.

In addition, to reduce error in data collection, a standard study eCRF will be used, ensuring a measure of consistency among the collectors.

Another limitation is coming from the diverse handling of data collection from deceased patients which is allowed without informed consent in some countries but not in all.

However, no country-based analyses will be done. Given the median overall survival (31.6 months in LUX-Lung 3) and that time from launch of Gi(l)otrif to data collection in the participating countries is shorter than the median overall survival (OS) the majority of the patients are expected to be alive.

External validity is provided by the global approach of this study and the broad inclusion criteria but limited to patients treated within the label and at the selected, experienced sites. Internal validity will be given by source data verification.

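### Section 9.2.1 enters all eligible patients yet caps each site at 15, with no start date or order to decide which 15 enter where a site has more

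*Protocol*

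**What the plan says.** Protocol section 9.2.1 gives two inclusion statements and a limit:

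- The opening rule makes entry consecutive: "All consecutive patients will be included if all the following criteria are present".
- The explanation after the exclusion criteria makes entry complete: "All patients fulfilling inclusion and exclusion criteria from a site will be entered to avoid bias".
- The limit comes straight after that explanation, with a reason of its own: "The maximum of 15 patients per site was chosen to avoid bias by high proportion of patients coming from one site".

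Section 9.2 sets the scale at about 25 to 30 sites and gives the expected number at each: "An average of 8-10 patients per site (with a maximum of up to 15 patients per site) is expected".

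Sections 9.9 and 9.12 describe the safeguard against selection bias in softer terms, as "the recommendation to include consecutive patients meeting each of the inclusion criteria and none of the exclusion criteria". Both add that the retrospective nature of the data may itself limit selection bias.

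On records, section 9.2.1 says "A log of all patients included into the study will be maintained". It provides no log of patients who were eligible but not entered. The only calendar condition in 9.2.1 is a launch date before 1 January 2015, and that condition selects countries and sites, not patients. The SAP contains derivations and date imputation and no selection rule.

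**The concern.** The protocol relies on complete or consecutive entry to keep selection from biasing the results. At a site with 16 or more eligible patients, complete entry is ruled out by the cap. Consecutive entry does not fill the gap, because a series needs a starting point and a direction. One site could enter its first 15 patients and another its most recent 15, and both could claim compliance.

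This matters more here than in a prospective study. Investigators abstract data from existing records (section 9.1), so the exposure (dose modification) and much of the outcome information (adverse drug reactions, stopping date, progression) can be seen when a patient is considered for entry. If entry at a capped site depended on what the chart shows, the adverse drug reaction percentages, the median times and the comparison with LUX-Lung 3 would describe a selected group. A patient passed over leaves no record, so the analysis could neither detect nor correct this.

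**Working it through.** **1. The rules side by side.** Let M be the number of eligible patients at a site. Entering all of them means M entries, and the cap means min(M, 15). The two agree only if M is 15 or less. For M above 15, M − 15 patients are left out and the documents do not say which.

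**2. The plan's own figures.** From section 9.2: 25 × 8 = 200, 25 × 10 = 250, 30 × 8 = 240 and 30 × 10 = 300. The planned minimum of 200 is the low end. With every site at the cap, the ceiling is 25 × 15 = 375 to 30 × 15 = 450. The cap therefore does not threaten the study size; the issue is only who enters.

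**3. Could a site exceed 15?** Section 7 gives first approvals on 12 July 2013 (US) and 25 September 2013 (EU). Section 6 starts data collection on 31 May 2016. If launch followed approval at once (an assumption), about 32 to 35 months are available, and 16 eligible patients need one start about every two months. If launch was as late as the end of 2014, about 17 months are available, and 16 patients need about one start a month. Sites are chosen because they prescribe regularly, so neither rate is far-fetched, but no actual rate is given.

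**4. How often the cap might bind.** The documents give no distribution of eligible patients per site. I assumed Poisson counts (sites vary only by chance) or negative binomial counts with size k (smaller k means more variation between sites). In each case I set the eligible mean m so that the mean of min(M, 15) equals the expected 8 or 10. Then:

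- share of sites above 15 = P(M > 15)
- share of eligible patients left out = 1 − (8 or 10)/m
- share of entered patients from sites above 15 = 15 × P(M > 15)/(8 or 10)

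| Entered average | Distribution | m | Sites above 15 | Eligible left out | Entered from those sites |
|---|---|---|---|---|---|
| 8 | Poisson | 8.0 | 0.8% | 0.2% | 2% |
| 8 | k = 5 | 8.3 | 8% | 4% | 15% |
| 8 | k = 2 | 9.1 | 16% | 12% | 30% |
| 8 | k = 1 | 11.0 | 25% | 27% | 46% |
| 10 | Poisson | 10.1 | 5% | 1% | 8% |
| 10 | k = 5 | 11.1 | 20% | 10% | 31% |
| 10 | k = 2 | 13.1 | 32% | 24% | 48% |
| 10 | k = 1 | 18.0 | 42% | 44% | 63% |

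For example, with k = 1 and an entered average of 10: 1 − 10/18.0 = 44% left out, and 15 × 0.421/10 = 63% of entered patients come from sites above 15.

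**5. Room for choice at one such site.** Take the 53% dose-reduction rate from LUX-Lung 3 (section 7) and an assumed M of 20, 25 or 30, giving 11, 13 or 16 dose-reduced patients. The smallest possible number of dose-reduced patients among 15 is 15 minus the number not reduced: 15 − 9 = 6, 15 − 12 = 3 and 15 − 14 = 1. The largest is 11, 13 or 15. The dose-reduced share could therefore lie anywhere in 40–73%, 20–87% or 7–100%. These are arithmetic limits on unrestricted choice, not forecasts.

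**6. Would it be seen?** The log lists included patients. Source data verification covers about 30% of included patients (sections 9.4 and 9.8), and each site is visited once, after data collection (section 9.2.2). None of these lists eligible patients who were not entered.

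**The case against.** The strongest reply is that 9.2.1 is the operative section and makes consecutive inclusion binding, 9.10.6 allows no waivers, and a sensible site would read the rules together as its first 15 consecutive patients. On this reading patients are left out without any regard to outcome. With 8 to 10 patients expected on average, the cap may bind at only a few sites. This largely stands as to frequency and intent. It does not supply the missing start date or direction, and it does not make compliance checkable.

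Several stronger readings are tempting, but the documents do not support them:

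- A reader might infer that investigators choose patients by outcome. The protocol does not tell them to; it leaves them able to, and only at sites above 15.
- A reader might take "the recommendation to include consecutive patients meeting each of the inclusion criteria" in 9.9 to mean that consecutive entry is optional. Sections 9.9 and 9.12 are narrative on limitations and bias, and the rule is in 9.2.1. The word needs aligning, no more.
- A reader might say that every outcome is known at selection. Patients still on treatment for at least 6 months are eligible and are censored at data collection (section 9.7.1), so their outcomes may be incomplete.
- A reader might add the loss of patients who died before they could consent. That is a separate mechanism, which the cap does not cause. Section 10.1.1 asks for consent waivers to avoid it, and 9.9 lists it as a limitation.
- A reader might conclude that every primary result is biased. No direction or size can be derived. Single-group summaries shift if entry depends on outcome; the dose-group contrast is at risk mainly if entry depends on dose group and outcome together.

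**Conclusion.** The conflict between entering all eligible patients and the cap of 15 is in the text and needs no assumption. So are the missing start date and order, and the log limited to included patients. Where a site has more than 15 eligible patients, the stated protection against selection bias does not operate, and a departure from it would leave no trace.

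The extent is unknown. The range of about 1% of sites and 0.2% of eligible patients (Poisson, average 8) to about 40% of both (k = 1, average 10) rests on assumed distributions, and no single figure within it can be defended from the documents. Whether any bias would follow, and in which direction, cannot be determined. The point should be corrected before data collection, because the analysis cannot repair it afterwards.

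**What to change.** In section 9.2.1, replace the statement that all eligible patients are entered with one binding, pre-specified rule that does not depend on outcome. For example: list eligible patients by date of first dose from a stated start date and enter them in that order, without skipping, up to 15. Another fixed order, or a random sample drawn from the full list, would also serve. Use the same rule in 9.9 and 9.12 in place of the word recommendation. Extend the site log to all eligible patients with the reason for any non-entry, and report the number not entered, overall and by site.

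The cap and the target of 200 are unchanged. The cost is protocol wording and a longer site log, since sites must list eligible patients before entering any. An earliest-first order also leans towards earlier starters, who are more likely to have died and so to meet the consent limitation in 9.9. This should be weighed when the order is chosen.

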9.2.2 Details of study procedures

The study procedures will consist of:

- Start of data collection:
Data of eligible and included patients will be collected after the site initiation visit (site initiation visit will be done in a virtual meeting). Data source is from existing data from patients' medical records.
- End of data collection:

After all data of eligible and included patients are collected, source data verification (SDV) will be completed and site close out visit will be performed. Sites will be visited once after data collection for SDV and closing visit.

9.3 VARIABLES

Data will be documented from the date of first dose of Gi(l)otrif[®] treatment until the date of last dose of Gi(l)otrif[®] treatment or end of data collection whichever occurs first.

During the data collection period, the following data will be collected from medical records in an eCRF by investigators during the study:

- Informed consent
- Diagnosis
- Demographics (gender, date of birth, ethnicity)
- Body weight and height at start of Gi(l)otrif[®] treatment
- ECOG performance score at start of Gi(l)otrif[®] treatment
- EGFR mutational subgroup (Del19/L858R)
- Starting dose of Gi(l)otrif[®]
- Start date of Gi(l)otrif[®] treatment
- End date of Gi(l)otrif[®] treatment
- Gi(l)otrif[®] dose modification(s) and date(s)
- ADRs
- Concomitant medications (limited to medication for management of diarrhea, skin effects, mucositis/stomatitis as dichotomous variables (e.g. received anti-diarrhea medication yes/no))
- Reason for dose modification(s)
- Date of progression
- Type of progression:
 - a. clinical
 - b. radiographic
 - c. both clinical/radiographic progression

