9.7 DATA ANALYSIS

9.7.1 Main analysis

All collected data will be analysed separately for patients starting with 40mg and \leq 30mg. Although due to anticipated low sample size in patients starting with \leq 30mg, it will be mainly for exploratory purpose. Baseline demographics will be analysed with descriptive statistics (N, median, mean, 25%, 75% percentile, SD) and compared descriptively between patients who have dose modifications within the first 6 months of Gi(l)otrif[®] treatment and those who do not. All the demographics, safety and efficacy data from this study in real-world setting will be compared with data from LUX-Lung 3 trial in descriptive manner.

Analysis of Safety:

[figure not shown]
Safety analysis will include all patients treated with Gi(l)otrif[®] and be descriptive in nature. Incidence and severity of ADRs according to Common Terminology Criteria for Adverse Events (CTCAE) criteria (version 4.0) ([R15-5988](#)) when available will be summarized and displayed in number/percentage. For patients who had Gi(l)otrif[®] dose modifications within the first 6 months of Gi(l)otrif[®] treatment, frequency and severity of the common ADRs pre- and post-dose modification will be analysed (\geq 40mg vs $<$ 40mg; and \geq 30mg vs $<$ 30mg). Missing or incomplete ADR dates will be imputed according to BI internal SOPs.

Analysis of Effectiveness:

Effectiveness analysis will include all patients treated with Gi(l)otrif[®]. Time on treatment is from the date of first dose of Gi(l)otrif[®] treatment to the date of last dose of Gi(l)otrif[®] treatment. Time to progression is from the date of first dose of Gi(l)otrif[®] treatment to the earliest date of documented progression (clinical, radiographic or both clinical/radiographic progression) or death. Time on treatment and time to progression will be estimated using Kaplan-Meier method, and the median along with two-sided 95% CI will be displayed (use the Greenwood's formula for estimation of standard errors). Log-rank test will be applied to compare between patients with and without dose modifications. Time on treatment and time to progression will be compared between patients who dose reduced to $<$ 40 mg within the first 6 months of Gi(l)otrif[®] treatment and those who remained on Gi(l)otrif[®] 40 mg once daily. This is in analogy to the analysis made on LUX-Lung 3 where a cut-off of 6 months was used as most dose reductions occur during this time.

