In the analyses of the two time-to-event endpoints, missing or incomplete data are managed by standard survival analysis techniques. For patients still on treatment, time on treatment will be censored at the date of data collection. For patients still on treatment and without progression, time to progression will be censored at the date of data collection. For patients stopped treatment and without progression/death or progression/death date missing, time to

progression will be censored on the last contact date.

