9.10.4 Patient completion

The collection of the data of patients will continue until end of data collection or withdrawal of consent which occurs first.

At the earliest of the above criteria, the Patient Completion information should be completed in the eCRF.

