## 1 Methods for calculation of derived variables

Age at registration: Year of registration [patient.birthyear] – Year of birth [registration.registered\_at]

Drug-related AE: All AE with relationship to Gi(I)otrif® [ae.gilotref\_relation\_1='yes']

Time on treatment: Date of last administration [endofobservation.date] - Date of first administration of Gi(I)otrif® [baseline.date]. For patients still on treatment, time on treatment will be censored at the date of data collection.

Time to progression (TTP): First date of progression [min(endofobservation.radio\_date, endofobservation.clinic\_date)] - Date of first administration of Gi(I)otrif® [baseline.date]. Patients not known to have a progression will be censored with the date of last contact. For patients still on treatment and without progression, time to progression will be censored at the date of data collection. For patients who stopped treatment and without progression or progression date missing, time to progression will be censored on the last contact date.

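### Protocol 9.3 closes documentation at last dose, yet time to progression needs progression, death and last-contact dates after it; events are lost if sites follow 9.3

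*Protocol*

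**What the plan says.** **Window.** Protocol 9.3 (Variables) documents data from first dose until the last dose of "treatment or end of data collection whichever occurs first". The list that follows includes start and end dates of treatment and date and type of progression. It has no date of death and no date of last contact.

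**Endpoint.** Protocol 9.7.1 (Main analysis) ends time to progression at the "earliest date of documented progression (clinical, radiographic or both clinical/radiographic progression) or death", without restricting this to time on treatment. For patients who stopped with no event, or with no event date, time to "progression will be censored on the last contact date".

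**Other text on the window.** Protocol 9.10.4 (Patient completion) says: "The collection of the data of patients will continue until end of data collection or withdrawal of consent which occurs first". Last dose is not a stopping point there. Protocol 11.2 requires fatal adverse events in the eCRF until the end of the study, but only from signature of consent.

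**SAP.** Section 1 takes the event from the "First date of progression" alone, so death is not an event. It keeps the last-contact rule: "For patients who stopped treatment and without progression or progression date missing, time to progression will be censored on the last contact date". It names no data field for last contact, and it takes the date of last administration from the end-of-observation date.

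**The concern.** A rule that censors stopped patients at last contact presupposes information after last dose, and so does an endpoint that counts any later progression or death. A window that closes at last dose supplies neither. The patients affected are those who stop before progression, for example for intolerance. Protocol 9.2.1 deliberately keeps patients who stopped before 6 months, in order to avoid bias.

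This is a primary outcome. It is set beside LUX-Lung 3, where median PFS was 11.3 months in patients who reduced dose in the first 6 months and 11.0 months in those who did not (Protocol 7). It is also compared by log-rank test between patients with and without dose modification. If later events are missing, time to progression is overstated. Tolerability plausibly drives both dose reduction and stopping, so the loss need not be equal in the two groups.

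**Working it through.** **1. The texts side by side.** Protocol 9.3 names both last dose and end of data collection and takes the earlier, so last dose overrides. Protocol 9.10.4 names end of data collection and withdrawal of consent only. The endpoint and censoring rule in 9.7.1 can be carried out under 9.10.4 but not under 9.3. Even under 9.10.4, the 9.3 list lacks the death and last-contact dates that 9.7.1 uses. Fatal adverse events under 11.2 do not close the gap: in a retrospective chart study many deaths may precede consent, and consent may be waived.

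**2. Inputs for the size.** The plan has no figure of its own to reproduce here, and its 200 patients rest on feasibility and not on an event count. All of the following are assumptions: exponential on-treatment progression with median 12 months (λ = ln 2 / 12 = 0.0578 per month); a share f of 5-25% stopping before progression through a competing exponential hazard λf/(1−f); a post-stop hazard m times λ, with m from 1 to 2; follow-up uniform over 6-33 months.

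**3. Formulas.**
- Event-free survival with full follow-up, writing x = λt and r = 1/(1−f): S = e^(−rx) + [f/(1−f)]/(m−r) × (e^(−rx) − e^(−mx)). With m = 1 this is e^(−x), median 12.0.
- Censored at last dose: Kaplan-Meier estimates the on-treatment hazard λ, so the median is 12.0 whatever happens after stopping.
- Post-dose events unrecorded and censored at last contact, with contact running to data collection: Kaplan-Meier estimates 1 − (1−f)(1 − e^(−rx)). The median is −ln[1 − 0.5/(1−f)] × (1−f)/λ. For f = 0.25: ln 3 × 0.75 / 0.0578 = 14.26.

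**4. Overstatement of the median, in months.**

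| Stop before progression | Full median, m = 1 | Full median, m = 2 | Last-dose censoring, m = 1 | Last-dose censoring, m = 2 | Last-contact censoring, m = 1 |
|---|---|---|---|---|---|
| 5% | 12.0 | 11.83 | 0 | 0.2 | 12.29 − 12.00 = 0.3 |
| 10% | 12.0 | 11.65 | 0 | 0.35 | 12.64 − 12.00 = 0.6 |
| 15% | 12.0 | 11.47 | 0 | 0.5 | 13.06 − 12.00 = about 1 |
| 25% | 12.0 | 11.08 | 0 | 0.9 | 14.26 − 12.00 = 2.3 |

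With m = 2, last-contact censoring overstates by the sum of the last two columns, because the true median is lower.

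**5. Events lost per 200 patients.** Average the event probabilities over follow-up of 6-33 months.
- f = 5%, m = 1: 128.4 events with full follow-up, 125.2 recorded; 3.2/128.4 = 2.5% lost.
- f = 25%, m = 2: 135.8 with full follow-up, 110.2 recorded; 25.6/135.8 = 18.8% lost.

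**6. Sensitivity to the set-up.** A second simulation used medians of 11.0 and 13.6 months (Protocol 7), first dose uniform over the 30 months before data collection, the exclusion of patients still on treatment under 6 months, and 5-20% stopping. It lost about 2-14% of events. With the 11.0-month input and 20% stopping:
- last-dose censoring gave 10.4 against 10.4 months (m = 1) and 10.4 against 9.7 (m = 2);
- last-contact censoring gave 11.7 against 10.4 (m = 1), and at 10% stopping 10.9 against 10.4.

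With the 13.6-month input, 20% stopping and m = 1, last-contact censoring gave 14.5 against 12.9.

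**The case against.** The strongest reply is that the documents do not establish that data stop at last dose. Protocol 9.10.4 says otherwise. The second sentence of 9.3 has the listed items, date of progression among them, collected during the data collection period. The SAP takes separate radiographic and clinical progression dates and assumes that a last-contact date exists. This stands: the loss depends on which text sites follow. It does not remove the conflict, because 9.10.4 can also be read as the 2016 abstraction period, leaving 9.3 to set the clinical window.

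A second reply is that the bias may be nil. With an unchanged post-stop hazard and censoring at last dose, events are lost but the median does not move. That also stands. But neither document states last-dose censoring. Under the last-contact rule that both state, unrecorded progression adds event-free time and lengthens the median without any informative stopping.

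A third is that Protocol 9.9 expects most patients to be alive, so few death dates would be missing. That limits the death component and leaves progression after stopping untouched.

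A reader might infer that patients who stop for toxicity definitely lose their events, or that the dose-reduction comparison is biased in a known direction. The documents support neither. The first depends on site practice. For the second, no group-specific stopping rates are given and no direction has been calculated.

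**Conclusion.** The inconsistency is real and concerns a primary outcome. Protocol 9.3 does not fit 9.7.1, contradicts 9.10.4, and omits two dates that the endpoint and its censoring rule need. Any progression or death after last dose falls outside the literal 9.3 window, whatever the reason for stopping.

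The size is conditional on sites following 9.3 and on assumed inputs. With 5-25% stopping before progression, a 12-month on-treatment median and a post-stop hazard of 1-2 times, about 2.5-19% of events are lost. Under last-dose censoring the median is overstated by 0 months (hazard unchanged) to about 0.9 months (hazard doubled, 25% stopping). Under last-contact censoring with an unchanged hazard, it is overstated by about 0.3, 0.6, 1 and 2.3 months at 5%, 10%, 15% and 25% stopping. Those last figures assume that contact runs to data collection, and an earlier last contact would shrink them.

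An unequal effect on reducers and non-reducers is plausible but not quantified. The planned size of 200 is unaffected. The matter should be settled before data collection starts.

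**What to change.** - Reconcile Protocol 9.3 with 9.10.4. State in 9.3 that progression, death and last contact are documented after last dose, up to the date of data collection, whether or not treatment has stopped. ADR and dosing data may still close at last dose.
- Add date of death and date of last contact to the eCRF list in 9.3, and name the last-contact field in SAP section 1.
- Align the SAP event (progression only) with the Protocol event (progression or death). Otherwise a recorded death date would not enter the SAP analysis as an event.

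The cost is two date fields, one sentence in 9.3, a matching edit to the SAP and slightly more chart abstraction per patient.
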